12.4 Supplementary Analysis Plans

12.4.1 Secondary endpoints

Secondary endpoints will be decisional quality, as measured by the DCS and Decisional Regret; clinical time required; patient QOL, which will be measured by questionnaires and converted into continuous summary scores using standard algorithms; and utilization, which will be categorized by the type of treatment the patient received, as determined by chart review at 12 months post-diagnosis. We will also consider the primary outcome of knowledge within only minority men (pooled) (defined as non-White or Hispanic White), as well as separately within the three racial subgroups. It is worth noting that some patients may receive a follow-up biopsy before these secondary endpoints are measured (at 12 months after first consultation), which could have a strong impact on their DCS and QOL scores. Thus, whether or not a patient receives a follow-up biopsy before 12 months (and the timing of this biopsy) will be taken into account when modeling these endpoints.

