8.2.4 Consultation

Arm A: The physician or appropriate clinical staff (e.g., physician assistant) will incorporate the during-consultation decision aid in his/her conversation with the patient about treatment choice. In addition, the physician or appropriate clinical staff will engage the patient regarding any questions by the patient about the pre-consultation decision aid. Site staff will record the time that the patient spends with the pre-consultation decision aid.

Arm B: Usual care, and the physician or appropriate clinical staff will engage the patient regarding any questions by the patient regarding the pre-consultation decision aid. Site staff will record the time that the patient spends with the pre-consultation decision aid.

Arm C: The physician or appropriate clinical staff will incorporate the during-consultation decision aid into his/her conversation with the patient about treatment choice.

Arm D: Usual care.

All Arms: At the end of the consultation, the physician will remind the patient that the study coordinator has post-visit (baseline) questionnaires for the patient to complete. The study coordinator will also assess the time for the consultation, which will be recorded in a separate field on the data collection forms. This will be defined as the time from when the physician enters the consultation room to when physician's consultative activities end (i.e., when the physician leaves the room OR when the patient is handed off to the CRA to complete post-consultation forms).

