10.2 Decisional Conflict Scale (DCS)

The decisional conflict scale was developed and validated by O'Connor⁷² as an instrument intended to “elicit 1) health-care consumers' uncertainty in making a health-related decision; 2) the factors contributing to the uncertainty; and 3) health-care consumers' perceived effective decision making”. The low literacy version of this questionnaire will be used, and it contains 10 items answered on a 3 point scale (i.e., “yes,” “unsure,” “no”) and may be adapted to specific health-care decision scenarios. Example questions include agreement with the following statements: “Did you know which options were available to you?” “Did you know the benefit of each option?” “Did you feel sure about what to choose?”.

The questionnaire will be administered once, immediately after the consultation (post-consultation). It is estimated that it will take participants approximately 5-7 minutes to complete this questionnaire.

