10.3 Expanded Prostate Cancer Index Composite Short Form (EPIC-26)

The Expanded Prostate Cancer Index Composite⁶⁶ measures health-related quality of life and returns summary scores for urinary, bowel, sexual, and hormonal domains with high test-retest reliability and internal consistency.

The questionnaire will be administered once; 12 months after the patient's initial consultation. The instrument contains 26 items, and will take approximately 10-15 minutes to complete.

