12.2.1 Analysis Plan

Although the randomization unit will be participating site, our inferential unit for statistical analysis will be the individual patient. Due to the potential for correlation among patients within the same site, a mixed effects regression model (also known as random effects model or multi-level model) will be utilized to examine the effects of the during-consultation Prostate Choice and the pre-consultation Knowing Your Options decision aids. Specifically, this model will contain a fixed intercept, a fixed effect for having received Prostate Choice, a fixed effect for having received Knowing Your Options, and a random, site-specific intercept to allow patients within the same site to be correlated. Baseline patient-level characteristics including race, ethnicity, severity of disease and site-level characteristics may be incorporated in this model if deemed appropriate. A similar approach will be utilized in the statistical analysis of secondary endpoints. Furthermore, descriptive statistics will be reported after incorporating cluster information, in particular, the empirical cluster size, and the observed intra-cluster correlation.

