12.4.2 Secondary analyses

Decisional quality, average clinical time required, and patient QOL scores will be compared across DA types using linear mixed models similar to that used to assess the primary endpoint. In particular, this model will include fixed effects for Prostate Choice and Knowing Your Options and a random, site-specific intercept to allow for subjects within the same site to be correlated. Utilization will be compared across DA types using a generalized linear mixed model, again with fixed effects for having received Prostate Choice and having received Knowing Your Options and a random, site-specific intercept.

As mentioned above, the primary analysis will be re-implemented within only minority men as a secondary analysis. We anticipate enrolling approximately 80% minority men. It is worth noting that, if this were the primary analysis, this sample would give us approximately 78% power to detect an absolute difference of 8% in knowledge for either of the decision aid main effects using a two-sample t-test (with two-sided alternative) with a 2.5% significance level (i.e. the same analysis/assumptions used to power the primary analysis).

As an additional secondary objective, we will explore whether the overall effects of interventions on patient knowledge, quality of life, and treatment utilization differ by racial/ethnic subgroups. Our sample size is driven by the primary outcome of knowledge. Oversampling of minority populations of interest will achieve a robust representation of these minority populations in our final sample, but we have not designed the trial to have sufficient power to ascertain subtle subgroup differences in knowledge and quality of life by race/ethnicity subgroups. These secondary analyses will be exploratory, because fully testing the racial/ethnic differences would require prohibitively large sample sizes, and the literature does not suggest a strong race-based rationale for large differences. If subtle but potentially important trends in subgroup differences are identified in these exploratory analyses, those findings could be used to justify a larger study examining a primary hypothesis related to racial/ethnic difference or could influence the design of subsequent culturally tailored interventions. At present, the science of decision aids and the state of the evidence surrounding racial/ethnic differences in the effect of decision aids would not support testing such a hypothesis as a primary endpoint.

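### Follow-up biopsy, a post-randomization event, enters the secondary-endpoint models in an unstated way, and the reason given cannot apply to the Decisional Conflict Scale

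*Combined protocol and SAP*

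**What the plan says.** Section 12.4.1 lists the secondary endpoints as DCS, Decisional Regret, clinic time, quality of life and treatment utilization. It then notes that some men may be biopsied again "before these secondary endpoints are measured (at 12 months after first consultation), which could have a strong impact on their DCS and QOL scores". It concludes that whether "a patient receives a follow-up biopsy before 12 months (and the timing of this biopsy) will be taken into account when modeling these endpoints".

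Section 12.4.2 specifies the models. For decisional quality, clinic time and quality of life, "this model will include fixed effects for Prostate Choice and Knowing Your Options and a random, site-specific intercept". For the remaining endpoint, "Utilization will be compared across DA types using a generalized linear mixed model", with the same fixed and random terms. Neither model has a biopsy term. Section 12.2.1, whose approach is carried over to the secondary endpoints, offers one kind of addition: "Baseline patient-level characteristics including race, ethnicity, severity of disease and site-level characteristics may be incorporated in this model if deemed appropriate". Neither section rules biopsy out.

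On timing, 10.2 says of the DCS: "The questionnaire will be administered once, immediately after the consultation (post-consultation"). Section 10.3 says of EPIC-26: "The questionnaire will be administered once; 12 months after the" initial consultation; 10.4 says the same of Decisional Regret. On clinic time, 8.2.4 says: "The study coordinator will also assess the time for the consultation, which will be recorded in a separate field on the data collection forms".

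**The concern.** There are three problems.

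1. **The adjustment is not defined.** It could be a covariate, a stratification or a sensitivity model. Nothing says how biopsy timing enters for men who had no biopsy. The endpoints covered could be the DCS and quality-of-life scores only, or everything listed in the section. Two analysts could fit different models and both claim to follow the plan.

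2. **Biopsy is a post-randomization variable.** A site's arm is fixed before its patients enroll (4.3), and follow-up biopsy comes after the consultation at which the aid is used. Objectives 2.2.1 to 2.2.3 ask for the effect of the aids on quality of life and utilization. If the aids alter who is biopsied, conditioning on biopsy can remove part of that effect, or create an apparent effect where none exists.

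3. **The stated reason fails for the DCS**, which is already on record before any follow-up biopsy takes place.

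**Working it through.** The plan gives no figure on this point, so there is none to reproduce. The check compares timings, then illustrates the mechanism on assumed inputs.

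**Timing**

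| Endpoint | When recorded | Could a biopsy in the following 12 months affect it? |
|---|---|---|
| DCS | Once, right after the consultation (10.2; 5.0 note 2) | No |
| Clinic time | At the consultation (8.2.4) | No |
| EPIC-26 | Once, at 12 months (10.3; 5.0 note 3) | Yes |
| Decisional Regret | Once, at 12 months (10.4; 5.0 note 3) | Yes |
| Utilization | Chart review at 12 months (8.3.2) | Biopsy may be part of, or follow from, the treatment path itself |

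Section 12.4.1 dates these endpoints at 12 months without distinction. That does not hold for the DCS or clinic time. Its rationale names the DCS, but not Decisional Regret, which is measured at 12 months.

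**How bias could arise.** Section 1.3 says the aids are meant to align treatment with disease risk, and active surveillance is a utilization category (8.3.2). A route from aid to treatment choice to biopsy is therefore plausible. It is our inference: the documents give no biopsy rate and no link between surveillance and biopsy.

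**Illustration 1 (every input assumed).** Half the men receive an aid. Active surveillance is p0 = 0.30 without it and p1 = 0.45 with it. Surveillance men score 10 points better. Only they are re-biopsied, with probability q. Biopsy itself changes the score by d points. Least squares in the population gives:

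- Without biopsy in the model: effect = (p1 - p0)(10 + dq).
- With biopsy in the model: effect = 10(p1 - p0)(1 - bq), where b = [p0(1 - p0) + p1(1 - p1)] / [p0(1 - p0q) + p1(1 - p1q)].
- Gap (adjusted minus unadjusted) = -(p1 - p0) q (10b + d), which is zero at d = -10b.

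For q = 0.4: b = (0.21 + 0.2475)/(0.264 + 0.369) = 0.723, so the adjusted effect is 1.5 × (1 - 0.4 × 0.723) = 1.07.

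| | q = 0.4 | q = 0.6 | q = 0.8 |
|---|---|---|---|
| Adjusted effect (any d) | 1.07 | 0.78 | 0.44 |
| Unadjusted, d = 0 | 1.50 | 1.50 | 1.50 |
| Gap, d = 0 | -0.43 | -0.72 | -1.06 |
| Gap, d = -5 | -0.13 | -0.27 | -0.46 |
| Gap, d = -10 | +0.17 | +0.18 | +0.14 |
| d at which the gap is zero | -7.2 | -8.0 | -8.9 |

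If the aid raises surveillance by 10 points instead of 15, the gaps run from -0.72 to +0.11; by 5 points, from -0.36 to +0.05; with no shift they are 0.

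**Scale.** With 172 men at 20 sites (8.6 per site) and the plan's intra-site correlation of 0.1, the design effect is 1 + 7.6 × 0.1 = 1.76. The main-effect standard error is sqrt(4 × SD² × 1.76 / 172). For an assumed SD of 15 to 30 this is 3.03 to 6.07 points, so the largest gap is 1.064/3.03 = 0.35 down to 1.064/6.07 = 0.18 standard errors.

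**Illustration 2 (every input assumed).** One million men were simulated. Biopsy use is 20% without the aid, the aid has no direct effect, and results are in residual SD units.

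- Biopsy use also 20% with the aid: adjusted and unadjusted estimates agree.
- Biopsy use 30% or 40% with the aid, and biopsy lowers the outcome by 0.5: the total effect is -0.05 or -0.10, and the adjusted effect is 0.00.
- Biopsy use 30% or 40%, biopsy harmless, but an unmeasured factor drives both biopsy and outcome: the true effect is 0, and the adjusted effect is -0.04 or -0.08.
- Both mechanisms together: they largely offset, with a difference of about 0.01 or 0.02.

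**Utilization.** In illustration 1, every re-biopsied man is on surveillance, so a logistic model for surveillance has no finite biopsy coefficient. The aid's odds ratio is (0.45/0.55)/(0.30/0.70) = 1.91 with or without biopsy. The difficulty there is estimation, not bias. This treats a three-category endpoint as binary.

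**The case against.** The best defense is that nothing shows a biased estimate will be reported. Bias needs both a main analysis that conditions on biopsy and aids that change biopsy use. The section that defines the models has no biopsy term, and taking biopsy into account could mean a sensitivity analysis. The second condition rests on an inferred route. This stands, and the bias is claimed only under those conditions. But 12.4.1 says biopsy will be taken into account in modeling and nowhere calls this a sensitivity analysis.

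A second objection is that the endpoints meant are naturally the 12-month scores, not clinic time or utilization. That is a fair reading, but the text names the DCS, which is not a 12-month score, so the reader cannot rely on it.

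Third, biopsy timing may matter for a sound reason. Most EPIC-26 items ask about the last four weeks (Appendix II), and a recent biopsy might disturb the answers briefly. That supports a stated secondary model that looks at timing. It does not support placing biopsy in the main estimate.

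Fourth, the size is small and assumed. With 140 men (7 per site, design effect 1.6) the standard error is 3.2 to 6.4 points and the largest gap is 0.17 to 0.33 standard errors. This is accepted; the point rests on the rule, not on the size.

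**Conclusion.** The concern holds. Two parts need no assumption: the form and scope of the biopsy adjustment are not stated, and the rationale is wrong for the DCS. The third part is conditional. If the main estimate conditions on biopsy and the aids change biopsy use, it is not the total effect on the 12-month outcomes, and the direction of the difference is not known in advance. The documents do not allow the bias to be sized, and on the assumed inputs it is a fraction of a standard error. Only secondary endpoints are involved; the knowledge endpoint, sample size and design are unaffected. It should be corrected before analysis.

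**What to change.** In 12.4.1 and 12.4.2:

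- State that the 12.4.2 models, without biopsy or any other post-randomization covariate, are the main analysis for EPIC-26, Decisional Regret, DCS, clinic time and utilization.
- Keep any biopsy-adjusted model as a labelled exploratory or mediation analysis. Name the endpoints it covers and state how biopsy and its timing enter.
- Report follow-up biopsy by arm.
- Remove the DCS from the biopsy sentence, and correct the 12-month dating, which does not hold for the DCS or clinic time.

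The cost is a few sentences and no design change. The downside is that variation due to biopsy stays in the residual.

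Reporting biopsy by arm needs complete capture. Section 5.0 note 1 limits the chart review to months 6 to 12, while 8.3.2 gives no start date. These should be reconciled so that biopsies in months 0 to 6 are recorded. The case report forms are not in the documents and may already cover this.

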12.4.2 Secondary analyses

Decisional quality, average clinical time required, and patient QOL scores will be compared across DA types using linear mixed models similar to that used to assess the primary endpoint. In particular, this model will include fixed effects for Prostate Choice and Knowing Your Options and a random, site-specific intercept to allow for subjects within the same site to be correlated. Utilization will be compared across DA types using a generalized linear mixed model, again with fixed effects for having received Prostate Choice and having received Knowing Your Options and a random, site-specific intercept.

As mentioned above, the primary analysis will be re-implemented within only minority men as a secondary analysis. We anticipate enrolling approximately 80% minority men. It is worth noting that, if this were the primary analysis, this sample would give us approximately 78% power to detect an absolute difference of 8% in knowledge for either of the decision aid main effects using a two-sample t-test (with two-sided alternative) with a 2.5% significance level (i.e. the same analysis/assumptions used to power the primary analysis).

As an additional secondary objective, we will explore whether the overall effects of interventions on patient knowledge, quality of life, and treatment utilization differ by racial/ethnic subgroups. Our sample size is driven by the primary outcome of knowledge. Oversampling of minority populations of interest will achieve a robust representation of these minority populations in our final sample, but we have not designed the trial to have sufficient power to ascertain subtle subgroup differences in knowledge and quality of life by race/ethnicity subgroups. These secondary analyses will be exploratory, because fully testing the racial/ethnic differences would require prohibitively large sample sizes, and the literature does not suggest a strong race-based rationale for large differences. If subtle but potentially important trends in subgroup differences are identified in these exploratory analyses, those findings could be used to justify a larger study examining a primary hypothesis related to racial/ethnic difference or could influence the design of subsequent culturally tailored interventions. At present, the science of decision aids and the state of the evidence surrounding racial/ethnic differences in the effect of decision aids would not support testing such a hypothesis as a primary endpoint.

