1.4 Description of Interventions to be tested

Decision aids can be delivered within or prior to specialty visits using a variety of modes, including paper, tablet, and computer-based platforms. Decision aids delivered prior to the clinical visit prepare patients for decisions by providing information to have a basic understanding of facts discussed in a clinical consultation. Members of our team [REDACTED] have extensive

experience testing decision aids outside of the clinical visit. Most of the decision aid literature tests them prior to provider visits; these trials improve knowledge, but do not necessarily improve patient-provider communication.^{44,45,53-55} The Mayo Clinic team typically tests decision aids for use with the clinical visit. These tools are minimal detail props to promote a better conversation. Several clinical trials of decision aids delivered within visits show improvement in patient knowledge comparable to tools delivered prior to consultation.^{56,57} In contrast to tools delivered prior to the visit, tools delivered within a visit may promote better patient involvement in decision making. How the two forms of decision aid delivery might combine to improve outcomes is also uncertain. Despite the promise of decision aids, they are rarely used in specialty practice for prostate cancer and in-visit decision aids have never been tested as a tool to mitigate both disparities in knowledge as well as in functional outcomes for prostate cancer.

Whether in-visit and out-of-visit decision aids potentiate each other in enhancing decisional quality is an additional important unaddressed question that could inform eventual larger scale health services implementation strategies in underserved patient populations with PCa.

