2.2 Secondary objectives

- 2.2.1** To test the impact of in-visit DA's alone compared to usual care on quality of life outcomes and treatment utilization.
- 2.2.2** To test the impact of out-of-visit DA's alone compared to usual care on quality of life outcomes and treatment utilization.
- 2.2.3** To test the impact of combined in-visit and out-of-visit DA's compared to both usual care and individual DAs on quality of life outcomes and treatment utilization.
- 2.2.4** To test the comparative effectiveness of DA's on minority men's knowledge.
- 2.2.5** To compare clinic time required to administer the DA's across arms.

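### The main-effects-only secondary models answer four of the five arm comparisons in objectives 2.2.1 to 2.2.3 only if the two aids act additively

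*Combined protocol and SAP*

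**What the plan says.** Section 2.2 states three objectives as comparisons between arms. Objective 2.2.1 reads: "To test the impact of in-visit DA's alone compared to usual care on quality of life outcomes and treatment utilization". Objective 2.2.2 asks the same question of the pre-consultation aid. Objective 2.2.3 takes the two aids together, "compared to both usual care and individual DAs on quality of life outcomes and treatment utilization".

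Section 12.4.2 then gives the models. For decisional quality, clinic time and quality of life it is a linear mixed model: "this model will include fixed effects for Prostate Choice and Knowing Your Options and a random, site-specific intercept". The generalized linear mixed model for utilization has the same structure: "again with fixed effects for having received Prostate Choice and having received Knowing Your Options and a random, site-specific intercept". Section 12.2.1 had already said of the primary model: "A similar approach will be utilized in the statistical analysis of secondary endpoints". None of these places has a product term, a four-level arm factor or a list of arm contrasts.

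Two other sections bear on additivity. Section 12.2.2 says that an interaction is not expected, that power for it would be inadequate, and that it will be left out of the primary analysis. Section 1.4 says: "Whether in-visit and out-of-visit decision aids potentiate each other in enhancing decisional quality is an additional important unaddressed question".

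**The concern.** Two main effects and no product term force the fitted effect of the combination to equal the sum of the two single-aid effects. Each aid then has one coefficient, which is its effect averaged over presence and absence of the other aid. The plan would have to use that one number both for the aid alone against usual care and for the gain from adding it to the other aid. Objectives 2.2.1 to 2.2.3 treat these as separate questions.

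Non-additivity is plausible from the protocol's own description. Sections 1.4 and 1.5 present two tools for the same decision, and both tailor risk to disease severity and take up quality of life across treatments. If their content overlaps, the averaged coefficient understates what either aid does alone and overstates what a second aid adds. If they reinforce each other, both errors reverse. Either way, the comparison of the combination with single aids, which matters for deciding whether to deliver both, would rest on an assumption that the analysis never examines.

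**Working it through.** **Inputs.** Arm labels follow Section 8: A both aids, B pre-consultation aid only, C during-consultation aid only, D usual care (Section 1.5 uses B and C the other way round). Section 12.2.2 gives a standard deviation of 12 points, a difference of 8 points, a two-sided level of 0.025, an intra-site correlation of 0.1 and 20 sites. Section 12.3.1 gives 172 patients, 43 per arm. The SD, difference and correlation are for knowledge. The plan gives no such figures for quality of life or utilization, so borrowing them here is an assumption.

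**The plan's own figure.** For 50 against 50 independent patients, SE = 12 × √(2/50) = 2.40 and 8/2.40 = 3.33. The noncentral t calculation gives 85.3% power, which reproduces the stated figure of about 85%.

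**What the additive model estimates.** Let Prostate Choice alone add a, Knowing Your Options alone add b, and both add a + b + γ, where γ is the interaction. With equal arms, the Prostate Choice coefficient is ½[(C − D) + (A − B)] = ½[a + (a + γ)] = a + γ/2. Likewise, the Knowing Your Options coefficient is b + γ/2. Hence:

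| Contrast | Objective | True value | Model reports | Error |
|---|---|---|---|---|
| C − D | 2.2.1 | a | a + γ/2 | +γ/2 |
| B − D | 2.2.2 | b | b + γ/2 | +γ/2 |
| A − D | 2.2.3 | a + b + γ | a + b + γ | 0 |
| A − B | 2.2.3 | a + γ | a + γ/2 | −γ/2 |
| A − C | 2.2.3 | b + γ | b + γ/2 | −γ/2 |

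**Illustrations, with a = b = 8.**

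- Full overlap, γ = −8: the model reports 4 for each aid alone (true 8), 4 for combined against single (true 0), and 4 + 4 = 8 for combined against usual care (true 8). Taking usual care as 0, the fitted arm means for D, C, B, A are 2, 6, 6, 10; the true means are 0, 8, 8, 8.
- Potentiation, γ = +8: the model reports 12 for each aid alone (true 8), 12 for combined against single (true 16), and 24 for combined against usual care (true 24).

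**Where recovery of A − D weakens.** With γ = −8 and arm weights A/B/C/D of 6/4/5/5, the model gives 7.67 against a true 8. With 3/7/5/5 it gives 9.22. On a logit scale, I took a binary outcome with equal arms, no site effect, and proportions of 0.2 in D and 0.4 in each of the other arms. The A − D log odds ratio is then 0.894 against a true 0.981, and C − D is 0.447 against a true 0.981.

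**Precision of direct contrasts.** With 172/20 = 8.6 patients per site, the design effect is 1 + 7.6 × 0.1 = 1.76, and 172/1.76 = 97.7 effective patients.

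- Main effect: SE = √(4 × 144/97.7) = 2.43.
- Arm against arm: SE = √(8 × 144/97.7) = 3.43, a ratio of √2 = 1.41.
- Interaction: SE = √(16 × 144/97.7) = 4.86.

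| Power for 8 points | Level 0.025 | Level 0.05 |
|---|---|---|
| Main effect | 84% | 90% |
| Arm against arm | 51% | 63% |
| Interaction | 28% | 38% |

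These figures ignore the small between-site degrees of freedom and so are optimistic.

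**The case against.** The strongest defence is that additivity is declared. Section 12.2.2 says interactions are not expected, Section 1.3 presents the design as studying individual and additive effects, and Section 12.2.1 carries the same approach to secondary endpoints. If additivity holds, the two coefficients answer all five contrasts, four of them more precisely than direct comparison of arms would. This stands, but it has limits. Section 12.2.2 discusses the knowledge endpoint and excludes the interaction only from the primary analysis. Section 1.4 treats potentiation as an open question, although it does so for decisional quality, which objectives 2.2.1 to 2.2.3 do not name.

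There is also a bias-variance argument. The additive estimate of a single-aid contrast has the smaller mean squared error while (γ/2)² is below 3.43² − 2.43², that is, until the interaction exceeds about 2 × 2.43 = 4.9 points on the borrowed figures. This is a good reason not to replace the planned model. It is not a reason to leave the named contrasts without a direct estimate.

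A reader might infer that any departure from additivity makes every comparison with the combination wrong. The documents do not support that: with 43 per arm as planned, the linear models reproduce combined against usual care exactly, and its standard error is the same under either approach. Nor do they support a forecast that the trial will recommend a redundant second aid. The plan gives no figure for an interaction, and the 8-point example only shows the mechanism, on the knowledge scale.

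**Conclusion.** The mismatch between objectives and models is real, and it is confined to secondary endpoints. Each aid alone against usual care, and the combination against each single aid, are four of the five named contrasts and are valid only under additivity. In the balanced linear model the error is otherwise exactly half the interaction, upward or downward according to its sign, and the fitted coefficients do not reveal it. For the utilization model the half-interaction rule is only approximate. Combined against usual care is sound in the linear models under equal allocation, and approximate under unequal arms or for utilization. Section 12.3.1 acknowledges that imbalance between arms can arise. The structural result rests only on the stated models. The point sizes and power figures rest on the borrowed knowledge SD of 12 and correlation of 0.1. The two primary main-effect tests are not affected.

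**What to change.** In Section 12.4.2, keep the main-effects models and state that their results assume the aids act additively. Leave the primary tests as they are. Add a prespecified supplementary analysis of the quality-of-life and utilization endpoints, and optionally of decisional quality and clinic time, using a four-level arm factor. This is equivalent to adding the product of Prostate Choice and Knowing Your Options. Keep the random site intercept. Report the four arm means and the five contrasts in 2.2.1 to 2.2.3 with confidence intervals, labelled as estimation.

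The change needs no new patients or data. Its cost is extra analysis, wider intervals for the four single-aid contrasts, and more comparisons across endpoints. The text should say that power is low and that a non-significant interaction is not evidence of additivity.
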